### C. APPROACH

**Overview of study procedures.** This study will be implemented as a roll-out trial, a commonly used approach in system-wide intervention designs. During the JID intake process, all juveniles attend their appointment with a caregiver/legal guardian and complete the MAYSI-2 and PQ-B. Youth will be eligible to participate in the study if they flag on either the caution (2 items endorsed) or warning (3 or more items endorsed) cut-offs on the 5-item MAYSI-2 Thought Disturbance subscale, or the cut-off score (> 6) on the PQ-B. Using both measures will allow us to examine rates of false positives on the MAYSI-2, which is commonly used in juvenile justice settings, enhance identification of females at risk, which is a relative weakness of the MAYSI-2, but not the PQ-B, and collect data on the PQ-B with this population, adding to the database of this commonly used measure in NIMH-funded studies (Personal communication, PO [name]).

JID intake workers will contact the research team when a youth screens in. As a back-up system, the JID workers turn in their MAYSI-2/PQ-B forms to the RIFC Mental Health Clinic (MHC) each day so the mental health team can determine if any further mental health evaluation is necessary for endorsement of any symptom. Co-Is [name] and [name] will be involved in this process so that if a youth who screened in on the Thought Disturbance subscale was not referred by the JID intake worker, they will be contacted by research staff if they signed the consent to contact form. Co-I [name], the Research Coordinator, or an RA, both of whom will have an office in the RIFC MHC on the same hallway as the JID, will consent/assent families. Research staff will be registered as court interns which will allow access to court records and the court calendar. Co-I [name], who also has an office in the MHC, will be the back-up for approaching families.

Because there are several research projects being conducted in the RIFC JID, Co-I [name] has established a procedure whereby all families in the waiting room are approached by an RA and asked to sign a "consent to contact" form. If a parent signs this form, and the teen subsequently screens positive and qualifies for a study being conducted in RIFC after the JID intake worker administers the MAYSI-2/PQ-B, research staff will then meet separately with parent/caregiver and the juvenile to describe study procedures in detail and 1) obtain juvenile assent without parental presence (note: no juvenile will ever be sanctioned by the court for not agreeing or being unable to participate in the research study; see Human Subjects/RIFC Chief Judge Letter of Support), and 2) obtain written informed consent from the parent/caregiver. If the research team is unable to meet with the family while they are at their intake appointment, the family will be contacted by phone/text and an appointment, either at the RIFC or at the family home, to consent/assent the parent and teen, and conduct the baseline assessment. Consenting procedures will also include permission to access court records.

**Intervention condition overview.** The intervention will have two phases: 1) a Standard Care (baseline control) condition, followed by, 2) an Enhanced Referral/Linkage to Care condition. Because this is a roll-out trial, the two conditions will be compared using a non-randomized open trial design. **Design Consideration:** We decided against randomization due to the following reasons: a) use of front line workers, as opposed to research staff specifically employed for the purposes of the research study, could result in contamination across the two study conditions; b) randomization would create the potential for therapist characteristics having a primary effect on referral outcomes; and c) JJS administrators and staff, at this site have expressed concerns that randomization is an unacceptable practice in the JJS because it results in the denial of what is assumed to be a superior service, the Enhanced Referral condition, to 50% of the youth.

Families approached in **months 3 - 14** (n = 100; 12 months of recruitment) will be in the standard care, baseline control condition and receive standard court procedures, with one exception. If the youth screens positive on the Thought Disturbance subscale or PQ-B, the intake worker will be instructed to refer the family to the CSC, rather than their local mental health clinic.

During **months 6 - 17**, follow-up assessments of the standard care group will be completed and in **months 18 - 19**, JID intake workers will be trained in the Enhanced Referral/Linkage to Care protocol as will the CSC staff who receive the referral from JID intake workers.

Youth consented in **months 20 - 31** (n= 100; 12 months of recruitment), will receive the Enhanced Referral/Linkage to Care protocol. Details regarding the content of this condition are described below.

**Design Consideration:** We considered enrolling an older sample because we will likely identify a larger proportion of prodromal (CHR) rather than syndromal psychotic disorder youth in juvenile justice. Nonetheless, this application's approach is consistent with FOA language, specifically in "better signal detection of psychosis onset, or symptoms suggesting high clinical risk of psychosis, within .... criminal justice agencies," as well as

*“methods to achieve expeditious referral of persons with first episode psychosis (FEP), or those at high clinical risk of psychosis”. As specified in the FOA, this planning grant application will also: “explore the occurrence of psychosis-spectrum symptoms”.*

We also considered having staff from the RIFC MHC perform a full evaluation before referring to the CSC but MHCs are not consistently associated with JJS nationwide so we opted for a procedure that would be generalizable to the JJS nationwide. Similarly, we considered having CSC staff meet the family at the JID but again felt this would not be a typical service delivery approach and consequently would affect eventual dissemination of our protocol.


The assembled research team collectively brings expertise in the assessment of adolescents with a broad range of psychopathology, including psychosis-spectrum disorders, experience in conducting community-based research, and experience in improving assessment and referral within the juvenile justice system.

**Participants.** JJS offenders, ages 12- 17, will be eligible for enrollment with the following criteria: 1) legal guardian available to consent for juvenile’s participation, and adolescent assents to participate; 2) juvenile is English speaking; parents may be Spanish-speaking because we will have Spanish-speaking research staff and interpreter services available; and 3) juvenile flags positive on the MAYSI-2 Thought Disturbance subscale or the PQ-B. Exclusion criteria include: 1) observable developmental delays that would interfere with obtaining assent and/or accurate assessment, and 2) juvenile meets hospital level of care for imminent risk due to severity of symptoms, in which case they will be transported to Emergency Department per existing JID procedures. In addition, we will collect a comparison sample (n = 70) meeting these same inclusion/exclusion criteria with the exception that they will screen negative on the MAYSI- 2 Thought Disturbance subscale and PQ-B. This subgroup will be used in analyses exploring the sensitivity/specificity of the MAYSI-2 Thought Disturbance subscale and PQ-B.. The MAYSI-2 is a 52-item self-report measure for ages 12-17 that screens for current MH symptoms. The Thought Disturbance Subscale consists of 5 items, 4 of which refer to altered perceptions of reality and the fifth to de-realization. The developers do not recommend use of the subscale with girls. *The PQ-B, a 21 item measure for both males and females, with an 8th grade reading level and takes 3-4 minutes to complete. In a sample of 141 adolescents and young adults referred for assessment to prodromal research centers, the instrument achieved specificity of 0.68 and sensitivity of 0.88 with regard to SIPS diagnoses using a cutoff distress score threshold of six or greater on the weighted distress measure. A recent review indicated sensitivity ranging from .70-.97 across different samples*.

**Racial and ethnic minority considerations.** Consistent with 2016 RIFC statistics, ethnic representation will be approximately 18% Hispanic and racial representation will be about 22% African American or Black

(and other) and 72% White. Consistent with US nationwide statistics, African American juveniles are disproportionately represented (22% of juvenile offenders, yet only 6% of the entire Rhode Island population). Approximately 9% of intake cases involve parents who speak only Spanish (see Facilities & Enrollment Table). Females are increasingly represented in the system (29% in 2016) and are disproportionately represented among status offenders (account for 46% of status offenses relative to 11% of violent offenses). We expect our sample to reflect these demographics, but we will over-sample girls if possible to lower the ratio of boys to girls.

**Estimated sample size and retention rates.** In 2016, the RIFC handled offenses for 2,634 juveniles of whom 764 (29%) were female and 2,581 (98%) who were in the 12-17 year old age range. The JID, for example, typically screens more than 900 juveniles per year and, of those youth who are screened, approximately 11% (N= 99) flag for thought disturbance. With a conservative enrollment rate of 70%, and 12 months of enrollment in both the baseline control (n = approximately 100 positive screens) and experimental intervention condition (n = approximately 100 positive screens), we would be able to meet our projected enrollment goals for both baseline standard care (n = 70) and enhanced referral (n=70) conditions. Using a conservative follow-up rate of 80% of the 140 enrolled and retained participants, approximately 55 families in both the baseline control and experimental condition are expected to complete the 3-month follow-up. In addition, we will recruit 70 youth in Phase I and Phase II who do not screen positive on the MAYSI-2 or PQ-B in order to conduct the sensitivity/specificity analyses. These projections are feasible given our excellent working relationship with the Rhode Island JJS including the RIFC and prior experience recruiting from the JID (see RIFC Chief Judge Letter of Support). Co-I [name] collaborated on a 24-month longitudinal epidemiological study of first-time CINI offenders at the RIFC and she successfully recruited the entire sample of 400 first-time offending CINI youth (DA034538). Co-I [name] is also currently recruiting at the RIFC JID for a baseline sample of suicidal CINI youth for her NIMH K23 Mentored Career Award. PI [name] also successfully established a referral system from RIFC to two completed grants, NIAAA (AA017659) and NIDA (DA0029871) trials for youth with substance use-related court involvement.

**Protection against attrition.** To maximize participant retention, we will employ procedures routinely used in our studies to reinforce with JJS families the value of the follow-up portion of the study and to use all available resources to locate participants. Contact information will include the names and phone numbers of two friends/family members who can be contacted if staff is unable to reach the teen. We will also ask for the parent and teen cell phone numbers and emails. Contact information will also be updated periodically prior to the 3-month follow-up assessment. Participants will also be given refrigerator magnets and pens with the program's contact information as well as a card with the date for the follow-up assessment. Reminder postcards, text messages, and emails will be sent to participants. Telephone calls will also be made to participants. Weekly case review meetings will be held with the PI and Co-Is to review no-shows and plans discussed to complete contact with the participant. We have used these procedures with success in prior projects. Participants will be contacted 1 week prior to their follow-up appointment. In PI [name]'s NIAAA-funded study with CINI youth, retention rates were 94% at 3 months and 84% at 6 months.

**Compensation for participation.** Families will be compensated \$100 for each assessment (\$50 each, for a parent and the teen, at baseline and 3-month follow-up).

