**Aim 1: Identify baseline prevalence of psychotic disorders and psychosis-risk syndromes within the JJ system.** We will calculate the percentage of youth who screen positive on the MAYSI-2 Thought Disturbance subscale and/or *PQ-B* over the 2-year period of the study. We will also calculate mean, median, and range of DUI/DUP in months, for both sub- and full- threshold psychosis. Correlations and regression techniques will be used to explore the relation between attenuated psychosis (both individual symptoms and syndromes) and co-occurring symptoms (BPM symptomatology; MINI symptoms and diagnoses). Prevalence estimates will make use of a weighted sample that takes into account the selection probability for SIPS evaluation given MAYSI-2 and *PQ-B* results, so that our results are generalizable back to the population of JJS youth. We will also examine the utility of the MAYSI-2 Thought Disturbance subscale and *PQ-B* as screeners for psychosis-spectrum syndromes and disorders by determining the criterion-related validity (e.g., sensitivity, specificity, positive and negative predictive value) of number of items endorsed for predicting psychosis risk, as confirmed by clinical interview with the SIPS, as well as compare the two screens. This analysis will also use the weighted data from the MAYSI-2 and *PQ-B* and SIPS evaluation sample, and logistic regression procedures.

**Aim 2A: Examine whether an enhanced referral procedure results in higher proportion of completed referrals to the CSC compared to standard referral procedures** by calculating the proportion of completed referrals in Phase I, standard care, versus Phase II, when an enhanced referral/linkage to care procedure is instituted in JJS. An 80% linkage will be considered a success, and reflects the expected linkage proportion in Phase II. The probability of linkage will be contrasted across phases using logistic regression procedures.

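### If girls are over-sampled as intended, the Aim 1 weights should include sex as well as the screen results, or the pooled prevalence may not generalise as claimed

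*Combined protocol and SAP*

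**What the plan says.** The paragraph on racial and ethnic minority considerations (section C, Approach) expects the sample to mirror court demographics, but adds that "we will over-sample girls if possible to lower the ratio of boys to girls". It gives no target ratio or sampling fraction.

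In the Data Analysis Plan, Aim 1, prevalence is to come from a sample whose weighting "takes into account the selection probability for SIPS evaluation given MAYSI-2 and *PQ-B* results". The declared purpose is that the estimates should hold for court-involved youth as a whole. Sensitivity, specificity and predictive values rest on the same weights: "This analysis will also use the weighted data from the MAYSI-2 and *PQ-B* and SIPS evaluation sample, and logistic regression procedures".

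Sex enters the analysis in three other places. The Significance section and the paragraph on sex as a biological variable promise results by sex, and the former adds an analysis of boys alone. The Aim 3B regression adjusts for sex. None of these alters the pooled Aim 1 estimates.

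**The concern.** Deliberate over-sampling makes sex a determinant of who receives a SIPS, alongside the screen result. Weights that account only for the screen result restore the right balance of screen-positives and screen-negatives, but leave too many girls within each group. If girls and boys with the same screen result differ in SIPS risk, the pooled estimate is pulled towards the girls' risk.

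Such a difference is plausible on the plan's own account. The Participants section notes that the MAYSI-2 developers advise against using the Thought Disturbance subscale with girls. The overview of study procedures describes detection of at-risk females as a weak point of that instrument. A given MAYSI-2 result may therefore mean different things in the two sexes.

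At stake are the Aim 1A prevalence, with its claim to generalise to the court population, and secondarily the Aim 1C accuracy measures.

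**Working it through.** **The plan's own figures** (estimated sample size and retention rates)

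- Girls: 764 / 2,634 = 29.0%. This covers all juveniles handled by the court in 2016; the share at the intake department, where screening takes place, is not given.
- Flags per year: 900 × 0.11 = 99. Enrolled per phase: 0.70 × 100 = 70 (0.70 × 99 = 69.3).
- Over two years: 1,800 screened, 198 positive, 1,602 negative. With 140 positives and 70 negatives given a SIPS, each positive stands for 198/140 = 1.4 youth and each negative for 1,602/70 = 22.9. If the text means 70 negatives per phase, each negative stands for 1,602/140 = 11.4.

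These figures reproduce. The plan states no prevalence, weight or bias to check.

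**Formula.** With weights by screen result only,

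bias = Σ over screen groups s of P(s) × (girls' share in sample − girls' share in frame) × (girls' risk − boys' risk),

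with P(positive) = 0.11 and P(negative) = 0.89.

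**Assumptions (not in the documents).** Girls are 29% of each screen group. Risk is 40% in girls and 20% in boys among positives, and 4% and 2% among negatives (ratio 2).

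- True prevalence: 0.11 × (0.29 × 0.40 + 0.71 × 0.20) + 0.89 × (0.29 × 0.04 + 0.71 × 0.02) = 0.02838 + 0.02296 = 5.13%.
- Only negatives over-sampled, to 50% girls: 0.02838 + 0.89 × 0.03 = 5.51%. Bias +0.37 points, +7% relative.
- Both groups at 50% girls: 0.11 × 0.30 + 0.89 × 0.03 = 5.97%. Bias +0.84 points, +16%.
- Both groups at 40% girls: 0.11 × 0.28 + 0.89 × 0.028 = 5.57%. Bias +0.44 points, +9%.

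**Range, both groups at 50% girls**

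- Girls at half the boys' risk (figures above swapped): 6.81% becomes 5.97%, −0.84 points, −12%.
- Girls at three times the boys' risk (45% against 15%; 6% against 2%): 5.42% becomes 6.86%, +1.44 points, +27%.
- Equal risk within each screen group: bias is zero.

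**A marginal sex difference is not enough.** Let risk be 30% in positives and 3% in negatives for both sexes, with girls 50% of positives and 29% overall. Overall risk is then (0.055 × 0.30 + 0.235 × 0.03)/0.29 = 8.1% in girls and (0.055 × 0.30 + 0.655 × 0.03)/0.71 = 5.1% in boys. The second bracket of the formula is zero in both groups, so there is no bias.

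**Accuracy, ratio 2**

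- Both groups at 50% girls: sensitivity stays at 0.02838/0.05134 = 0.033/0.0597 = 55.3%; specificity moves from 91.4% to 91.8%; PPV moves from 0.258 to 0.300.
- Only negatives over-sampled: sensitivity falls to 0.02838/0.05508 = 51.5%; specificity hardly moves; PPV is unchanged.

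**Sampling error.** At risks of 30% and 3%, SE = √(0.11² × 0.30 × 0.70/140 + 0.89² × 0.03 × 0.97/70) = 1.9 points, or 1.4 points with 140 negatives.

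**Is 40–50% girls reachable?** Among positives, 99 × 0.29 = 28.7 flagged girls per phase. Half of 70 needs 35, more than exist. Even 40% needs 28, or 98% of them, against 42 of 70.3 boys (60%). PQ-B positives could enlarge this pool, because the 11% is a MAYSI-2 rate. Among negatives, 35 girls would be drawn from about 1,602 × 0.29 = 465.

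**The fix.** With ratio 2 and 50% girls in both groups, 20,000 simulated samples weighted by screen result and sex averaged 5.14% (true 5.13%). The SE was 1.77 points, against 1.86 with screen-only weights.

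**The case against.** The over-sampling is conditional and has no stated fraction, and the same paragraph expects the sample to reflect court demographics. If it does not happen, this bias does not arise. The weighting text is also a single sentence that does not expressly exclude other variables. Both points stand, and they make this an omission to close rather than a certain error. Yet an analyst who followed the stated rule after the stated over-sampling would obtain an uncorrected estimate.

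A reader might infer that the pooled prevalence is biased whenever risk differs by sex. That goes too far: a difference acting only through the screen result is already handled by the planned weights.

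A reader might also take the 16% figure as the expected error. It needs 50% girls among screen-positives, which the recruitment figures make unlikely. Over-sampling would fall mainly on screen-negatives, where the illustration gives about 7%. The 29% is court-wide too. The intake department handles first-time offenders, and girls account for 46% of status offences, so its female share could be higher. For a given sampled share, the bias would then be smaller.

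Finally, sex-specific tabulations, if screen-weighted, would not carry this bias and could be recombined to the frame. That limits the harm, but nothing in the plan says it will be done for the pooled estimate.

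**Conclusion.** The point holds conditionally. If girls are over-sampled, and SIPS risk differs by sex within a screen group, the pooled weighted prevalence will not generalise as claimed. With girls at an assumed twice the boys' risk, 50% girls sampled and a 29% female frame, the overstatement is about 7% relative (0.37 points) when only screen-negatives are over-sampled. It is up to about 16% (0.84 points) when both groups are. Both are under one standard error. Only the threefold-risk case, at 1.44 points, comes close to one SE, and then only with 140 screen-negatives. The risks and sampled shares are assumptions.

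A reader might infer that the accuracy results are undermined to the same degree. The calculations do not support this. Under equal over-sampling with a common risk ratio, sensitivity is unchanged and specificity moves by about 0.4 points. Sensitivity shifts by about 4 points when over-sampling is unequal between the groups. PPV shifts only if positives are over-sampled, which the recruitment figures leave little room for.

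This is a modest, systematic and avoidable bias in a headline aim of a planning study, and worth a cheap correction.

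**What to change.** During recruitment, record the number screened and the number with a SIPS by screen result and sex. In the Data Analysis Plan, Aim 1, define each weight as the inverse of the realised sampling fraction in the participant's screen-result × sex cell. Alternatively, post-stratify to the sex distribution of all screened youth. Use these weights for prevalence, sensitivity, specificity, PPV and NPV.

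The cost is about one sentence in the plan and a running count. All youth are screened and research staff already review the forms daily, so the counts are within reach; they may be harder to rebuild afterwards. The statistical cost is possibly more variable weights. Precision did not suffer in the simulated case, but that gain is not general, and sparse cells may need collapsing. If girls are not over-sampled, the weights return to nearly the planned ones.

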#### **Referral Conditions**

**Phase I, months 3 – 14: Standard Care (baseline control) condition.** In the Standard Care condition, if a teen has a positive screen on the MAYSI-2/PQ-B screening battery, JJS staff members determine whether there is need for further evaluation or concern of imminent risk. If there is concern for imminent risk, then the staff member contacts a clinician in the RIFC Mental Health Clinic for an emergency evaluation. If the teen is not at imminent risk, a referral to a community mental health clinic is arranged by the JJ intake worker. In this application, we will follow the same procedures, but if there is no imminent risk, the JID staff member will refer to the CSC rather than a community mental health clinic. *The CSC will evaluate the teen and offer services at the CSC if psychotic symptoms are a primary concern. CHR youth with other primary issues (e.g., trauma, substance use) are typically seen by other services in the mental health clinic which houses the CSC. All CHR youth who consent to the study will be seen for follow-up assessments and can be referred back to the CSC or mental health clinic to resume/initiate treatment if symptoms worsen. In the data analysis, we will record the percentage of youth referred to the CSC who are CHR/psychosis risk, as well as the services they receive and clinical outcome data at the 3 month follow-up assessment.* Data collected by Co-I [name] indicates that 26% of the youth that present to JID report that they are already receiving mental health treatment. In such cases, the families will be referred back to their mental health provider with the recommendation to consult the CSC.

